#### **8.4.2 Unblinding procedures**

The blind of MP will not be broken except for the circumstance mentioned for emergency unblinding described above until the blind data review meeting [BDRM] has convened, the statistical analysis plan [SAP] of the MP has been finalized, and the database has been closed. After the blind of MP has been broken, the statistical analysis of results of MP will proceed, which will be documented according to GCP.

## 9 STUDY ASSESSMENTS AND VISIT SCHEDULE

### 9.1 Assessments

The following efficacy and safety assessments will be performed during this double-blind, randomized, parallel-group three arm dose-response study. The assessments on the AS used as efficacy variables will be performed by trained investigators only (see [Sections 9.1.1.1](#) and [9.1.1.2](#)). The assessment of AS must be performed after the assessment of GICSSs at week 4 of all treatment cycles of MP and OLEX. On days of injection visits, all assessments have to be performed prior to injection treatments. For standardization of laboratory test results, a central laboratory will analyze blood samples in this multi-center study.

An overall description of the study plan is provided in [Section 6.1](#) and in the Flow Chart in [Section 6.1.2](#). The time schedule of assessments is detailed in [Section 9.2](#). A tabular overview of study assessments is given in [Table 16](#) and [Table 17](#).

#### 9.1.1 *Clinical evaluations*

At the beginning of the study, information such as the subject's medical history, all past and concomitant medications within the last 4 weeks, phenol and alcohol injections within the last 6 months and BoNT medication regardless the time of administration prior to the Screening Visit will be recorded from the subject's file or from information given by the subject (if applicable) and the parent(s) ([Section 8.3](#)). Other data will be collected as required, including information obtained from physical and neurological examinations. The GMFCS level will be assessed as described in [Appendix 16.8](#). A review of this information will allow the investigator to assess whether the subject should be enrolled at the Screening Visit. Other screening data will be collected at the Baseline Injection Visit before decision for eligibility and randomization.

Instructions regarding assessments on the scales will be provided in a manual for investigators and will be trained at the investigators' meeting(s) before study start. The same investigator must perform the ratings on the AS at Baseline Injection Visit and Control Visit at Week 4 in MP. Also at all other site visits this investigator should preferably perform the AS ratings to reduce variability of assessments. Preferably the same investigator should interview the subject (if applicable) and the parent at all visits. Preferably, the same parent(s) or caregiver (if applicable) should rate on scales at all visits. Preferentially, all study visits are performed at a similar day time throughout the study to reduce variability of assessments.

---

 In subjects, living e.g. in a special-care unit permanently or most of the time with caregivers being his/her main social contacts, a caregiver may replace parent(s) for the assessment of the respective scales and measures,

Rating on the Investigator's GICS at Control Visit V3 must be performed by the same investigator, who had performed clinical assessment and evaluation of the subject at the Baseline Injection Visit V2.

The degree of spasticity may change over time, which can be caused either by the natural course of the disease or by treatment. In this clinical study, deterioration of the scores obtained from the scale ratings will generally not be considered as an AE as the score is an efficacy variable and will be biometrically analyzed as such. However, if the investigator considers the deterioration to be unrelated to the underlying disease and rather as an AE, this must be documented on the AE form in the eCRF.

#### 9.1.1.1 Ashworth Scale (AS)

The AS is a well-known and validated scale to categorize the severity of spasticity by judging resistance to passive movement [Ashworth 1964]. In the original and the modified version it is widely used to assess treatment effects of BoNT in clinical studies on adult spasticity [Simpson 1996, Pandyan 1999, Brashear 2002, Barnes 2010] and in many pediatric CP studies (for an overview see [Lukban 2009]).

A placebo-controlled phase 3 study with NT 201 in adults showed robust efficacy results using the original version of the AS [Kanovsky 2009]. This study will use the original form of the AS for efficacy evaluation.

Spasticity will be assessed on the following 5-point scale at visits as outlined in Table 16 and Table 17:

- 0 = No increase in tone.
- 1 = Slight increase in tone giving a "catch" when the limb was moved in flexion or extension.
- 2 = More marked increase in tone, but limb easily flexed.
- 3 = Considerable increase in tone - passive movements difficult.
- 4 = Limb rigid in flexion or extension.

In order to be enrolled, subjects must have an AS score of  $\geq 2$  points for elbow flexors or wrist flexors in at least 1 UL (see inclusion criterion in Section 7.2). For initiation of treatment in this study all chosen clinical patterns (UL and LL) must have an AS score  $\geq 2$  at the Baseline Injection Visit V2 of MP.

The passive movement of each treated joint will be carried out over a duration of about 1 s (1 s should be determined by counting "one thousand and one"). The assessment will be performed for no more than 3 consecutive times. All investigators involved in the

assessment on the AS must be trained for the rating in this study and training must be documented. A pre-study rater training session will be performed at the investigator meeting to reduce inter-rater variability throughout investigational sites. Any investigator who did not participate at the investigator meeting will receive training documents including a manual on AS assessment for self-study. Assessment of the AS must only be conducted by trained investigators.

The same investigator must perform AS assessment at Baseline Injection Visit V2 (before IP administration) and at Control Visit V3 at Week 4 of MP for an individual subject. The same investigator should preferably perform AS assessments at all other study visits in MP [REDACTED] for an individual subject.

It is mandatory for the investigator to assess the clinical patterns flexed elbow, flexed wrist, and clenched fist in the UL(s) selected for treatment. This means, that for unilateral UL treatment, these three patterns of the treated body side have to be assessed, whereas for bilateral treatment the three respective clinical patterns of both ULs have to be evaluated with the AS. Furthermore, the AS has to be utilized for each other treated UL or LL clinical pattern, such as thumb in palm, pronated forearm, pes equinus, flexed knee, and adducted thigh. An exemption is the clinical pattern extended great toe, for which no AS assessment has to be documented.

Limb positioning for each AS assessment will be described in an instructional outcome manual, must be documented with the AS assessment and also recorded in the eCRF. The limb positioning chosen for AS testing by the investigator in an individual subject at V2 has to be kept throughout study participation. Reasons for deviations from the initially chosen positioning e.g. newly developed contractures have to be documented in the eCRF.

#### 9.1.1.2 Global Impression of Change Scales (GICS)

The Global Impression of Change Scales (GICS) are subjective global outcomes to assess independently the investigator's, child's/adolescent's, and parent's or caregiver's (if applicable) impression of change due to treatment. Caregiver(s) may substitute parent(s) for the assessment of GICS, if they are main social contacts of subjects, e.g. in a special-care home.

At Week 4 of each treatment cycle in MP [REDACTED] the investigator, child/adolescent (if applicable), and parent(s) or caregiver (if applicable) evaluate the global change of spasticity separately in UL and LL (if applicable). The GICS will be provided in local language.

Since the Investigator's GICS is based on the clinical impression of the change due to treatment of the subject's spasticity compared to the condition before the last injection, the same investigator, who has performed clinical assessments at the Baseline Injection Visit V2 of MP must rate on this scale at Control. Visit V3 at Week 4 of MP. [REDACTED]

All assessments of GICS will be made before AS assessments in order not to be confounded by these assessments.

The question of the GICS for the investigator is:

‘Based on your clinical experience, what is your overall impression of change of the subject’s upper/lower limb spasticity due to treatment, compared to the condition before the last injection?’

Please check the one option that best fits your overall impression of change.’

For the GICS versions for child/adolescent and parent(s)/caregiver please refer to [Appendix 16.3](#). For children/adolescents and parent(s) or caregivers who are not willing or able to the self-assessment, the respective GICS versions will not be assessed. If children/adolescents can not self-complete the questionnaire due to e.g. motor abilities, the clinical staff can ask the GICS. Only one score for parent(s) or caregiver will be recorded in the eCRF even when more than one parent or caregiver is present at study visits. Therefore, parents/caregivers have to agree on the assessment or the assessment has to be delegated to one person.

The response option for all GICS versions is a common 7-point Likert scale that ranges from -3 = very much worse to +3 = very much improved:

- +3  Very much improved
- +2  Much improved
- +1  Minimally improved
- 0  No change
- 1  Minimally worse
- 2  Much worse
- 3  Very much worse

#### *9.1.1.3 Questionnaire on Pain caused by Spasticity (QPS)*

The QPS is a patient-reported outcome for children and adolescents (2-17 years) with CP on spasticity-related pain. A self-report version for the children/adolescent, an interview-version for the children/adolescent, and a proxy-report version for the parent(s)/caregiver are available for both UL and LL spasticity-related pain assessment. For this study, in addition to the UL versions that will be used for all subjects/parents/caregivers the LL versions will also be used for subjects with treatment combinations including UL and LL

treatment. While pain intensity is reported by the children/adolescents, pain frequency (based on observed pain behaviors) will be documented by the parent(s)/caregivers. Thus, the information provided by the children/adolescents complements the one of the parents/caregivers. Pain intensity and frequency of the QPS are assessed for general pain and for four different activity situations. The situations are described in different questions for rest, normal day activities, physical exercise and for an individually defined ‘very hard thing to do’.

The parent/caregiver version of the QPS should be always completed and always (if possible) from the same parent/caregiver throughout the study. Caregiver(s) may substitute parent(s) for the assessment of QPS, if they are main social contacts of subjects, e.g. in a special-care home. Based on the cognitive, communicative, and motor abilities of a subject, the QPS will be self-administered by the subject or the interview version will be used by the site staff. If no assessment by the subject is possible due to age or cognitive impairments, only the parent(s)/caregiver will complete their instrument version.

The assessment of spasticity associated pain by the subject or parent(s)/caregiver will be done at all personal visits in MP [REDACTED]. Only the QPS versions applicable for the chosen treatment combination (A-E) will be utilized (i.e. UL or UL and LL). The different final versions of the questionnaire are displayed in [Appendix 16.6](#).

[REDACTED]

[REDACTED]

[REDACTED]

[REDACTED]

[REDACTED]

[REDACTED]

[REDACTED]

#### *9.1.1.5 Investigator's Global Assessment of Tolerability*

The Investigator's Global Assessment of Tolerability is an estimation made at the end of treatment cycles in MP and OLEX. This evaluation bases on a 4-point ordinal scale proved useful in several phase 3 clinical studies conducted with NT 201 (see IB for additional information [[Merz Pharmaceuticals \(GmbH\) - IB](#)]).

The global assessment will be made on the following 4-point ordinal scale (see [Table 16](#) and [Table 17](#)):

- 1 = very good.
- 2 = good.
- 3 = moderate.
- 4 = poor.

The investigator will assess the scale at the Final Visit of MP V5, the End of Cycle Visits V9 and V13 and at the End of Study Visit (V17).

#### *9.1.1.6 Adverse Events and Adverse Events of Special Interest*

Subjects (if applicable) and parent(s) or caregivers (if applicable) will be requested to report all AEs to the investigator or site staff. It is the obligation of the investigator and/or any delegate to detect AEs by questioning the subject (if applicable) and parent(s) or caregiver(s) (if applicable) at each site visit or telephone contact.

For the detection of AESIs possibly indicating toxin spread, the investigator or delegate must actively question the subject (if applicable), the parent(s) or the caregiver (if applicable) at visits and TC. Caregiver(s) may qualify for being questioned for AEs/AESIs, if they are the main social contacts of subjects, e.g. in a special-care home. The questioning and documentation of answers will be standardized. To facilitate detection of AEs related to toxin spread active questioning for AESI will start before the 1st injection in this study at V2. Thereby, investigators will be able to detect pre-existing symptoms and conditions that could possibly confound AESI questioning. If an (S)AE is detected at AESI questioning at V2 this has to be recorded accordingly in the eCRF.

If a TC identifies a (S)AE/AESI that needs confirmation or treatment, (e.g., respiratory disorder, dyspnoea, aspiration, dysphagia, speech disorder, dysphonia, other signs of bulbar palsy or botulism) the investigator must schedule a Safety Visit [SV] in addition to the scheduled visits as soon as possible after the TC.

At injection visits, AE questioning will be done prior to and 30 min after injection treatment. (see [Section 10.1](#)).

All AEs observed throughout the course of the study must be documented in the eCRF. For definitions and details regarding documentation and reporting of AEs see [Sections 10.1 to 10.3](#).

#### **9.1.1.7 Physical and Neurological Examination**

The investigator will perform physical and neurological examinations for subjects at Screening Visit, at the Final Visit of MP and at the End of Study Visit (V17) (see [Table 16](#) and [Table 17](#)). The physical and neurological examination will cover standard physical and neurological examinations. Any abnormal findings will be documented in the subject's medical file. The investigator will confirm the conduct of these investigations in the eCRF.

#### **9.1.1.8 Vital Signs**

Vital signs (i.e., systolic and diastolic blood pressure, heart rate) will be assessed at each visit (see [Table 16](#) and [Table 17](#)). Vital signs will be recorded in sitting or lying position after the subject has rested for at least 5 minutes.

#### **9.1.1.9 Body Weight and Height**

Body weight (BW) and height will be assessed at Screening, at the Baseline Injection Visit V2, at the Final Visit of MP V5, at all Injection Visits of OLEX (V6, V10 and V14) and at the End of Study Visit (V17) (see also [Table 16](#) and [Table 17](#)).

### **9.1.2 Laboratory evaluations**

#### **9.1.2.1 Clinical and research laboratory evaluations**

Laboratory evaluations will be performed as possible for the age group of the subject. The bulletin of the World Health Organization [WHO] published a recent literature review on the blood sample volumes in child health research [[Howie 2011](#)]. The author concludes that blood sample volume limits ranging from 1–5% of total blood volume [TBV] within 24 hours and up to 10% of total blood volume over 8 weeks were

---

 If visits at the end of treatment cycle in MP or OLEX (i.e. V5, V9, and V13) and the Injection Visit of the following cycle (i.e. V6, V10, and V14) will be performed on the same day, BW and height can be transferred.

consistent with minimal risk to healthy children as far as limited evidence available may support any risk evaluation. However, lower limits for sick children seem advisable.

In this study, the lower limits mentioned for relevant age groups and weight classes in literature [[European Medicines Agency EMA 2008](#)] will be applied. Blood sample collection for clinical chemistry and hematology as well as for testing antibodies against BoNT will be restricted in frequency and volume. Limits will be set by the following assumption on the TBV and restrictions on maximum blood volumes withdrawn per time period:

TBV= 80 mL/kg BW

Maximum blood volume per withdrawal: 1% of TBV

Maximum blood volume withdrawn per 12 weeks: 3% of TBV

A central laboratory capable to properly handle the relatively small samples volumes (as compared to those usually obtained from adult subjects) will perform the analyses. The following blood (serum) volumes are necessary to result in sufficient samples for the respective tests:

- Clinical chemistry (including glucose, AP): 1.2 mL blood
- Hematology: 1.2 mL blood
- Fluorescence immunoassay [FIA]: 4.0 mL blood (1.5 mL serum)
- Hemidiaphragm assay [HDA]: 10.0 mL blood (4.0 mL serum)

#### 9.1.2.1.1 Clinical chemistry and hematology

Blood samples for the determination of clinical chemistry (including blood glucose and AP) and hematology will be drawn in volumes appropriate for the BW of the subject at Screening Visit (V1), at the Injection visit (V6) and at the End of Study Visit (V17).

Blood samples will be analyzed at a central laboratory that is capable to handle small volumes from pediatric samples. The amount of blood, number, kind and size of tubes, sample processing at the site as well as storage conditions will be specified in a separate instruction manual provided by the central laboratory. Depending on the involved countries and their county specific regulations, local laboratories could be involved as needed.

Clinical chemistry analysis includes the following serum parameters: sodium, potassium, creatinine, urea/blood urea nitrogen, alanine aminotransferase, aspartate aminotransferase, AP, gamma glutamyl transferase, total bilirubin, glucose, and total cholesterol. Based on lab values for creatinine and on the subject's height on the day of the blood draw the glomerular filtration rate [GFR] will be estimated [eGFR]. This calculation will be done using the "Schwartz" formula [[Schwartz 2009](#), [Schwartz 2009](#)].

Hematology will be assessed at the same visits as clinical chemistry. Hematologic analysis of EDTA blood comprises hemoglobin, hematocrit, erythrocytes (red blood count), leukocytes (white blood count), lymphocytes (absolute), monocytes (absolute), neutrophils (absolute), eosinophils (absolute), basophils (absolute), platelets.

Any laboratory result outside the normal range must be graded by the investigator or delegate as “abnormal, not clinically relevant” or “abnormal, clinically relevant”. A laboratory abnormality should be regarded as an AE if the investigator judges the value to be significantly worse than prior to study start or if relevant abnormal values are newly detected during the study, i.e., from signature of IC onwards. Relevant abnormal laboratory values should be recorded on the AE Form of the eCRF.

#### 9.1.2.1.2 Pregnancy Testing

In females with history of menarche (i.e., 1st menstrual bleeding), samples drawn for serum clinical chemistry will also be used to determine human chorionic gonadotropin at Screening and at the End of Study Visit (V17). On injection days (Injection Visits V6, V10 and V14), urinary pregnancy tests will be performed. If required by country-specific regulations, urinary pregnancy tests may also be performed at all other personal contacts in MP and OLEX (see also [Table 16](#) and [Table 17](#)).

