### Screening:

Screening Visit (V1): Day -14 (Week -2)  $\pm$  5 days

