Only for injection treatment of the LL(s), it will be allowed to change the LL patterns chosen at V2 in further treatment cycles. Regulations for doses per muscle, number of injection sites of [Table 15](#) and for total dose to the LL(s) must be respected.

It will not be allowed to change the treatment combination chosen at V2 or to change the body side of treatment in unilaterally treated subjects.

Only subjects meeting the following eligibility criteria will receive an NT 201 injection treatment in the 2nd to 4th cycle.

Eligibility Criteria	Rationale	Visits V5/6, V9/10 V13/14
1. Clinical need for injection of the main clinical patterns of the UL(s) treated in the previous treatment cycle with 8 U/kg BW NT 201 per UL (maximum dose of 200 U).	Safety concern; efficacy	X

Eligibility Criteria	Rationale	Visits V5/6, V9/10 V13/14

2. For subjects with combined UL and LL treatment in the previous treatment cycle (Treatment combinations B-E):            Clinical need for LL(s) treatment with dose of NT 201 used in the previous treatment cycle.
 
In B: Unilateral LL with 8 U/kg BW (maximum of 200 U) in subjects with unilateral UL treatment (GMFCS I-V).
 
In C: Bilateral LL with 12 U/kg BW (maximum of 300 U) in subjects with unilateral UL treatment (GMFCS I-III).
 
In D: Bilateral LL with 8 U/kg BW (maximum of 200 U) in subjects with unilateral UL treatment (GMFCS IV and V).
 
In E: Bilateral LL with 4 U/kg BW (maximum of 100 U) in subjects with bilateral UL treatment (GMFCS I-III).
	Safety concern; efficacy	X

3. AS score <math>\geq 2</math> in the treated clinical patterns. For subjects with an AS score of 1, the investigator will decide on the clinical need for reinjection.
	Efficacy	X

4. Agreement of investigator and subject (if applicable) and parent(s) on the need for reinjection.*
	Administrative	X

5. No infection and/or inflammation in the area of the planned injection points.
	Safety concern	X

6. Negative pregnancy test for female with history of menarche.**
	Safety concern	X

\* It is at the discretion of the investigator to decide whether reliable statements on the need for a reinjection can be obtained from the subject or have to be retrieved from a parent(s) only.

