## 7.3 Removal of subjects from treatment or assessment

### 7.3.1 *Discontinuation of subjects*

In accordance with the Declaration of Helsinki and the IC form, the subject or parent(s) may discontinue the study at any time without any penalty or loss of benefits to which the subjects is otherwise entitled (see [Section 7.4.3](#)). Both the discontinuation of study and the reason(s) why the study was prematurely discontinued must be recorded in the subject's file and the eCRF. Date and discontinuation circumstances should be stated. Further details on discontinuation could be documented in the respective section of the "End of Study" form of the eCRF.

Subjects must be discontinued from the study by the investigator at any time for any of the following reasons:

- Withdrawal of IC.
- Treatment with any other IP in another clinical study.
- Treatment with any BoNT other than study medication.
- Pregnancy (no further administration of IP(s), blood draw, or any other interventional procedure will be performed; see [Section 10.4](#)).
- Any AE for which treatment continuation would constitute an unacceptably high risk for the subject.
- AESIs of severe intensity that represent respiratory function disorders or swallowing disorders will trigger the premature termination of a subject without re-exposition to IP. The terms for these severe AESIs are:
  - AESI terms related to respiratory function disorders are aspiration, diaphragmatic paralysis, dyspnoea, pneumonia aspiration, respiratory arrest, respiratory depression, and respiratory failure.
  - AESI terms related to swallowing disorders are bulbar palsy, multiple cranial nerve palsies, dysphagia, hypoglossal nerve paresis, cranial nerve paresis, cranial nerve paralysis.
- Injection treatment cannot be performed for any reason, not even with local anesthesia and/or analgosedation.
- Eligibility criteria are not met after the previous injection of IP in the respective treatment cycle (MP or OLEX) (see [Section 7.3.1](#)).

The DMC may recommend further criteria for discontinuation. Deviations from this study protocol, or conditions comprising exclusion criteria established in [Section 7.3](#) that arise after the subject has been included in the study may (but will not necessarily) lead to the discontinuation of subject's study participation. All such conditions must be properly documented.

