**Table 14 Dose ranges for UL clinical patterns and muscles in the High, Mid and Low Dose Group of MP**

## **Injection treatment and post-injection measures**

NT 201 will be injected as intramuscular injection at the Baseline Injection Visit of MP and all Injection Visits of OLEX.

If needed, subjects will receive local anesthesia and/or analgosedation to reduce injection related pain and discomfort and to facilitate the injection procedure for the investigator. Analgosedation will be performed by qualified anesthesia personnel only. Procedures will include information of the subject and parent(s) before the start of analgosedation, medication with anesthetics, maintenance and monitoring (e.g., cardiovascular and respiratory). If analgosedation is intended to be used in a subject for the first time, fitness for analgosedation must be ensured first by a general pediatric examination. Fasting times required for some forms of analgosedation (e.g., nitrous oxide) have to be met.

Localization of the target muscle by palpation and anatomical landmarks alone was shown to be inaccurate, except for the gastrosoleus complex [Chin 2005]. To confirm the correct placement of the injection needle in this clinical study, all injections must be guided by at least one of three forms of technical guidance: ultrasound, electrical stimulation [e-stim], and/or electromyography [EMG]. Ultrasound will be the preferred guidance technique. All investigators performing injections of IP must be experienced in technically guided BoNT treatment of children and adolescents with CP.

The maximum dose per injection site should be 25 U NT 201 with a maximum volume of 0.5 mL per injection site for subjects of <25 kg BW. The maximum dose per injection site for subjects of  $\geq 25$  kg BW should be 50 U NT 201 with a maximum volume of 1.0 mL per injection site.

The investigator will use the IP and all study materials only within the framework of the clinical study and in accordance with this clinical study protocol.

Following injection of IP, the subject will be under observation for at least 30 min. The subject (if applicable) and parent(s) or caregiver(s) (if applicable) will be asked if any AE has occurred within the 30 min since injection.

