#### **8.2.4 Duration of treatment per subject**

The screening period before (baseline) injection treatment in MP lasts up to 2 weeks  $\pm$  5 days. In MP, subjects will receive one injection treatment followed by an injection-free observation period of 14 weeks  $\pm$  14 days (12 to 16 weeks, see Study Flow Chart in [Section 6.1.2](#)). After the Final Visit of MP, the subject will continue treatment in OLEX with up to three open-label treatment cycles. Therefore, the total study duration for a single subject is 50 to 66 weeks from Screening Visit to the end of the observation period (End of Study Visit V17). In OLEX cycles also, subjects should show need for reinjection 14 weeks  $\pm$  14 days after the previous injection.

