## **10.4 Pregnancy**

Each pregnancy that starts during the study must be reported by the investigator to the drug safety department of the CRO within 24 hours of learning of its occurrence (see [Section 10.2](#) for reporting address). Pregnancies and pregnancy follow-up should be reported on a pregnancy monitoring form. Pregnancies should be followed up until delivery. Pregnancy follow-up should describe the outcome of the pregnancy, including any voluntary or spontaneous discontinuation; details of the birth; the presence or absence of any congenital abnormalities, birth defects, maternal or newborn complications, and their relation to the IP. Each normal pregnancy has to be reported as a non-serious AE (drug exposure before or during pregnancy). Any abnormal pregnancy or pregnancy outcome has to be reported as SAEs. If pregnancy occurs before injection visits, the female will meet exclusion criteria. If pregnancy occurs after the 1st injection visit (V2), participation in the study will continue with all applicable visits until the end of the respective cycle (except invasive procedures such as blood drawing). A final examination (End of Study Visit, also except for invasive procedures such as blood drawing) should be performed at the end of the respective cycle. After the End of Study Visit the study participation will be terminated.

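### Section 9.1.2.1.2 mandates a urine pregnancy test on three of the four injection days and omits the first, V2

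*Protocol*

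**What the plan says.** Section 9.1.2.1.2 of the Protocol covers females with a history of menarche. It sets three rules:

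- Serum hCG is measured twice, from the clinical chemistry samples of V1 (Screening) and V17.
- A urine test is mandated for the open-label treatment days: "On injection days (Injection Visits V6, V10 and V14), urinary pregnancy tests will be performed".
- A urine test anywhere else is left conditional: "If required by country-specific regulations, urinary pregnancy tests may also be performed at all other personal contacts in MP and OLEX". The section then points to Tables 16 and 17.

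Four other places bear on this:

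- Section 8.1.1.2, under the heading on injection treatment: "NT 201 will be injected as intramuscular injection at the Baseline Injection Visit of MP and all Injection Visits of OLEX". The visit schedule in Section 6.1 names V2, Day 1, as that baseline injection visit.
- Section 7.2.1, criterion 6 for OLEX injections: "Negative pregnancy test for female with history of menarche". It applies at V5/6, V9/10 and V13/14, and its rationale is given as a safety concern.
- Section 10.4: "If pregnancy occurs before injection visits, the female will meet exclusion criteria".
- Section 7.3.1 lists pregnancy among the reasons for mandatory discontinuation, and adds that "no further administration of IP(s), blood draw, or any other interventional procedure will be performed".

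**The concern.** The rule is worded for injection days in general, but its list names only the three open-label ones. The first injection of the study is missing from it. Because the sentence that follows makes tests at all remaining contacts conditional on national regulations, a reader of this section would conclude that a V2 test is needed only where the country asks for one.

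The first dose is therefore held to a looser standard than the next three, and no reason is given. A site that follows this section literally, in a country without its own rule, could randomise and inject a post-menarche girl who was not found pregnant at Screening but is pregnant at V2. The protocol plainly does not want that, since Section 10.4 treats pregnancy before injection visits as exclusionary. Subjects up to 17 years are eligible, and the total dose at V2 can reach 20 U/kg, or 500 U from 25 kg upwards.

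**Working it through.** The plan states no figure on this point that could be reproduced. The check compares visit lists and does one interval calculation.

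**Step 1: count the injection days.** Section 8.1.1.2 and the visit schedule in Section 6.1 give V2, V6, V10 and V14, which makes four. Section 9.1.2.1.2 lists V6, V10 and V14, which makes three. V2 is the one left out.

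**Step 2: age of the last mandated test at V2.** On the readable text this test is the screening serum hCG. Screening is scheduled at Day -14 (Week -2) with a window of 5 days either way, and the first injection is on Day 1. The schedule equates Day -14 with Week -2 and has no Day 0, so the nominal gap is 14 days.

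- Shortest: 14 - 5 = 9 days
- Longest: 14 + 5 = 19 days

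Section 8.2.4 agrees on the upper end: "The screening period before (baseline) injection treatment in MP lasts up to 2 weeks", plus or minus 5 days. Because it is phrased as a maximum, the lower bound of 9 days rests on the visit schedule alone.

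**Step 3: set the four injection days side by side.**

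| Injection visit | Last test mandated in all countries (readable text) | Age of that test at dosing |
|---|---|---|
| V2 | Serum hCG at Screening | 9 to 19 days |
| V6 | Urine test on the day | 0 days |
| V10 | Urine test on the day | 0 days |
| V14 | Urine test on the day | 0 days |

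A same-day test is thus mandated on 3 of 4 injection days.

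**Step 4: allow for what cannot be read.** Table 16, the Main Period schedule, is not shown, and most exclusion criteria in Section 7.2 are blacked out. There are two possibilities:

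1. Neither requires a V2 test. The protocol then has a safety gap at the first dose.
2. At least one of them does. Section 9.1.2.1.2 then conflicts with it, because it lists three visits and makes the others depend on country rules.

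Both call for the same edit to Section 9.1.2.1.2.

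**The case against.** The strongest reply is that the safeguard may already exist where we cannot see it. Section 9.1.2.1.2 refers to Table 16, which is not shown. The exclusion table has a V2 column, and its criteria must be cleared before randomisation (Section 9.2). Surviving text suggests that a pregnancy criterion is among them: Section 10.4 says pregnancy before an injection visit meets the exclusion criteria, and a stranded footnote at the start of Section 7.2.1 defines menarche in essentially the same terms as the footnote to the OLEX pregnancy criterion. This stands to the extent that nobody can say the whole protocol lacks a V2 test, and that is not claimed here. It does not rescue Section 9.1.2.1.2, which is fully readable and gives an incomplete list.

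A second reply is that the two situations differ. V2 follows a serum test of about two weeks earlier. Without the urine tests, the last test before V6 would be that same screening sample, by then 12 × 7 + 9 = 93 to 16 × 7 + 19 = 131 days old. Serum before cycle 1 and urine before later cycles is therefore an arrangement one could defend. This also stands in part: V2 is not an untested dose, and the exposure is limited to pregnancies that begin or become detectable between V1 and V2. But it does not explain why a rule framed for injection days skips one of them, and the protocol offers no such justification.

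A third reply is that the harm requires a site to follow one paragraph and overlook the table and criteria. That is fair as a comment on likelihood, but it assumes the table and criteria contain the test. A mandatory safety procedure should not depend on the reader choosing the right one of two conflicting texts.

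**Conclusion.** The concern holds for Section 9.1.2.1.2. Its list covers 3 of the 4 injection days, and the wording leaves a V2 urine test to national rules. On the readable text, the latest mandated result at the first dose is 9 to 19 days old, against 0 days at each later injection.

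The size is modest. It affects only post-menarche females, whose number is not given, so no count of subjects at risk can be stated. No sample size, power or alpha figure changes. No effect on the Week 4 assessment is claimed either, because Section 10.4 keeps a pregnant subject in the applicable non-invasive visits to the end of the cycle. This is an inexpensive correction that should be made on patient-safety grounds. Confidence is medium, because Table 16 and the exclusion criteria decide whether it closes a real gap or only removes an inconsistency.

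**What to change.** In Section 9.1.2.1.2, add V2 to the bracketed list of injection visits, so that the mandatory urine test covers V2, V6, V10 and V14. State that a negative result is required before randomisation and injection at V2. Check Table 16 and the exclusion criteria in Section 7.2, and bring them into line where they do not already say this.

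The cost is a wording change plus at most one urine test per post-menarche female at V2, of the kind already used at the three OLEX injection visits. If Table 16 already schedules the test, there is no additional procedure.
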